### **Home Study Drug Administration**

All patients will consume one capsule every 12 hours for 5 days (total of 9 home doses). Patients will receive the medication at meal time, mixed with 30 mL of a room temperature non-carbonated liquid and ingested immediately to optimize probiotic viability. One extra dose/day will be provided (i.e. kits will contain 5 extra doses total of 15 capsules) to account for vomiting or wastage. The dose may be repeated once if vomiting occurs within 15 minutes of administration; this rarely happens more than once. Oral fluid therapy will be encouraged according to established guidelines.

### **Hospital Study Drug Administration**

We estimate that only a small proportion (<5%) of enrolled subjects will be hospitalized. If that does occur, subjects will continue on the study protocol as described for home study drug administration, as done in previous studies. Future unscheduled hospitalization at a non-study hospital site is even less common: none of the 274 patients enrolled in our pilot study were admitted to a different institution after evaluation. To minimize the impact that such an event could have on this trial, caregivers will be provided with a letter that they will be instructed to share with their pediatrician and with the admitting physician. The letter will describe the study, the care-plan, and it will include site investigator contact information and the importance of adhering to the study protocol.

## **4.3 Discontinuation of Study Drug**

Study drugs are sometimes discontinued because of intolerance or perception of a clinical adverse event from study drug administration. If any clinical abnormality, laboratory abnormality, intercurrent illness, new immunosuppressive therapy, or other condition occurs such that continued administration of study drug would not be in the best interest of the subject in the opinion of the investigator, study drug administration may be discontinued. When this occurs, regardless of the reason, the subject remains in the intention-to-treat

population, all data collection should proceed, and long term follow up for adverse events is carried out. Discontinuation of study drug will be documented and will be reported in the closed session of the next scheduled Data Safety Monitoring Board meeting. Clinical staff and parents should *not* report the early discontinuation of study drug to research staff who are conducting follow up data collection. The Principal Investigator should *not* be contacted by the site investigator, as intentional discontinuation of study drug implies a safety outcome, and the Principal Investigator should be blind to all study outcomes. *Discontinuation of study drug is not a withdrawal from the study.*

If study subjects are hospitalized after discharge to home from the emergency department, this is not a reason for discontinuation of study drug. We estimate that only a small proportion (<5%) of enrolled children will be hospitalized after discharge to home from the emergency department. If that does occur, subjects should continue on the study protocol unless they have developed an exclusion criterion for study drug administration (e.g. critical illness, immunosuppression, etc.). To facilitate continuation of study drug administration during hospitalization, parents are provided with a letter for their pediatrician. The letter will describe the study, the care-plan, and it will include site investigator contact information and the importance of adhering to the study protocol. The parents will be instructed to share this letter with their pediatrician and with the admitting physician.

Breaking the blinding of the study drug should not be necessary, but an unblinding procedure will be available. This will require contacting the Medical Monitor (PI of the Data Coordinating Center), who will have access to the study drug kit numbers. However, unblinding is almost never necessary. The primary anticipated reason for a clinician requesting unblinding is the suspected occurrence of invasive infection (bacteremia/septicemia or meningitis), and the natural desire to know if the subject was receiving active *Lactobacillus rhamnosus* GG, ATCC 53103 (LGG). The initial recommendation from the Medical Monitor will always be that the clinician should *assume* that the subject was receiving active drug, and include *Lactobacillus rhamnosus* in the differential diagnosis (and treatment coverage) of the suspected invasive infection. *Lactobacillus rhamnosus* is readily susceptible to common antibiotics, and the differential diagnosis of subsequent invasive infection would include organisms other than *Lactobacillus rhamnosus*. Thus, future clinical treatment should not be dependent on unblinding information.

If the situation requires unblinding, the Medical Monitor and Data Coordinating Center staff will provide the information, and the unblinding will be documented. Study drug will be discontinued, *but the subject should not be withdrawn from the study!* All study

procedures (except study drug administration) should be continued, as the subsequent clinical course of the subject is critical to the science of the trial. All unblinding events will be reported in the closed session of the next scheduled Data Safety Monitoring Board meeting. Clinical staff and parents should *not* report the unblinding to research staff who are conducting follow up data collection. The Principal Investigator should *not* be contacted by the site investigator, as intentional unblinding of a subject implies a safety outcome, and the Principal Investigator should be blind to all study outcomes.

#### 4.4 Withdrawal from Study

Parents may completely withdraw their child from participation in this study at any time, including discontinuation of data collection. However, withdrawal from study is a completely different issue from discontinuation of study drug, and true withdrawal from study is an exceedingly rare event. If parents demand withdrawal of their child from the study, research staff will attempt to obtain adverse event information as required by the Food and Drug Administration (all adverse events for 30 days, monthly follow up for long term adverse events).

#### 4.5 Stool Sample Testing

Stool sample swabs will be collected for polymerase chain reaction (PCR) analysis. Once obtained, swabs will be frozen and sent to a central laboratory for analysis. A storage and shipping protocol will be provided in the study manual of operations. Samples will be tested with multiplex PCR.

In addition, at the lead site, Washington University, study research personnel will collect and freeze subjects' bulk stool specimens in the acute phase (within 24 hours of presentation) and 14 days after presentation using a previously tested bulk stool specimen collection protocol. Specimens may be collected in the emergency department or the families will be given a specimen collection kit, gel packs and a metallic envelope. When the specimen is ready for collection, a courier will pick up the specimen and cool pack at the patient's home and deliver it to a logistics collection center at Washington University School of Medicine. This service is available 24 hours a day, year round. The stools will be stored as a part of a future project to assess the potential mechanisms of action of *Lactobacillus rhamnosus* GG, ATCC 53103 (LGG) in acute gastroenteritis.

## 5 Data Analysis

The hypotheses of this study are:

1. In children with acute gastroenteritis, probiotic administration in the emergency department will be associated with a clinically-important decrease in the proportion of children suffering from moderate-severe disease, defined by a validated Modified Vesikari Score  $\geq 9$ , compared to placebo.
2. In children with acute gastroenteritis, probiotic administration will not be associated with serious adverse events, and will have a similar rate of side effects (e.g. bloating, fever, abdominal distention) as compared to placebo-treated children.

All analyses will be undertaken by the intention-to-treat (ITT) principle, except for adverse events, which will use the as-treated principle (compare the subjects based on the treatment regimen that they received). Patients who drop out or inadvertently crossover will be followed and included in the ITT analysis. All statistical tests of hypotheses will be two-sided. Baseline characteristics will be analyzed to determine if there is a need to adjust for differences between groups in exploratory analyses. Sensitivity analyses will be performed to assess the possibility and consequences of non-random loss to follow-up. The proportions of children experiencing an unscheduled healthcare visit or any potential adverse effect, as reported by the caregivers, will be compared between groups using the Mantel-Haenszel test, stratified by site. The analysis will evaluate the presence/absence of pre-specified side effects, as an aggregate outcome variable. A per-protocol analysis will be conducted to provide additional insight as non-compliance may result in an underestimation of the benefits of probiotics in the ITT analysis.

### 5.1 Specific Aim Analyses

**Specific Aim 1.** Determine the clinical effectiveness of probiotic administration to reduce morbidity in children presenting to the emergency department with acute gastroenteritis.

The **primary efficacy endpoint** of this study is the presence of moderate-severe acute gastroenteritis, as defined by a total post-enrollment Modified Vesikari Score  $\geq 9$  during the 2-week follow-up period. Each of the 7 items in the score is tabulated individually (maximum of 20 points); the sum of these individual variables represents the total Modified Vesikari Score. At the time of randomization a baseline Modified Vesikari Score will be assigned based on symptoms prior to randomization. This baseline score will serve

as a covariate in a secondary analysis of the primary outcome. The post-enrollment Modified Vesikari Score which will be employed to determine the presence/absence of the primary efficacy outcome, is based only on symptoms that occur between randomization and day 14, the conclusion of the study period for this outcome. Only symptoms and outcomes that occur following randomization will be included in the post-enrollment score.

The post-enrollment score is calculated only once, on day 14. At that time, each of the seven variables will be assigned a score for the entire study period (from randomization to day 14). Each variable will be scored by 1 of 3 methods:

1. Worst 24 hour period - maximal number of episodes of vomiting in a 24 hour period, maximal number of episodes of diarrhea in a 24 hour period, and maximal temperature;
2. Total duration of symptoms, including the number of days on which any gastroenteritis-related symptom occurred;
3. Occurrence of a treatment outcome or unscheduled subsequent healthcare utilization. If the patient was admitted directly following their enrollment ED visit and that admission stay is longer than 48 hours, it will be included as treatment in the post enrollment MVS. If the patient's admission stay was less than 48 hours, it will not be included in any MVS calculation.

The primary efficacy endpoint (the presence of moderate or severe disease, as defined by a total Modified Vesikari Score  $\geq 9$  during the 2 week follow-up period) will be limited to symptoms and outcomes that occur after randomization. If a patient's symptoms of vomiting and diarrhea stop during the same 24 hours, and then recur, that is not included in the post-enrollment score since that will be considered a *new* illness. In the original score, severe disease was defined as  $\geq 11$  and moderate as  $\geq 9$ . In our derivation and validation pilot studies, construct validity was demonstrated and validated by using scores of  $\geq 9$  to define moderate and  $\geq 11$  to define severe disease. These cut-points were associated with significant increases in other measures of disease severity such as degree of dehydration, likelihood of admission and daycare ( $p = 0.01$ ) and parental work absenteeism ( $p < 0.001$ ).

The proportion of children with moderate-to-severe disease (i.e. Modified Vesikari Score  $\geq 9$ ), the primary outcome, will be analyzed by comparing proportions utilizing a Mantel-Haenszel test, stratified by participating center and by duration of symptoms at enrollment. Significance for this primary outcome measure will be set at 0.05. Secondary analyses of the primary outcome will use logistic regression methods to adjust for covariates

that may be imbalanced between groups, (e.g. age, pre-enrollment Modified Vesikari Score, hydration assessment, need for hospitalization at index visit). We will also analyze the outcome using Modified Vesikari Score as a continuous variable through a stratified Wilcoxon rank-sum test and compare the results with the primary analysis.

**Specific Aim 2.** Determine the safety and side effect profiles of *Lactobacillus rhamnosus* GG, ATCC 53103 (LGG) in children presenting to the emergency department with acute gastroenteritis.

The **primary safety endpoint** of this study is the occurrence of invasive disease (including meningitis and bacteremia) from *Lactobacillus rhamnosus*. The secondary safety outcome will be the presence of any adverse events. For more information on adverse events, see Section 8.3 on page 33. Adverse events (including serious) will be tabulated by study arm for DSMB reporting and for final analysis of the safety of *Lactobacillus rhamnosus* GG, ATCC 53103 (LGG) in this setting. Adverse events will also be coded using the MedDRA vocabulary.

## 5.2 Secondary Study Outcomes

Secondary outcomes will include three of the individual components of the Modified Vesikari Score considered independently and one additional measure of burden of illness. Specifically, they are:

1. **Diarrhea duration:** Time from randomization until the appearance of the last watery stool as reported during daily surveys.
2. **Vomiting duration:** Time from randomization until the last vomiting episode as reported during daily surveys. Vomiting duration is only evaluated in children who vomited  $\geq 3$  times during the 24 hours prior to the emergency department visit.
3. **Return visits:** Return visits for unscheduled care to a healthcare provider related to vomiting, diarrhea, dehydration, fever, or fluid refusal, within 2 weeks of the index visit. Scheduled visits (e.g. reassessment, vaccinations, unrelated issues) will not be included.
4. **Missed daycare:** Days of daycare missed by subjects who attend daycare.
5. **Missed work:** Days of work missed by caregivers who work outside of the home.
6. **Household transmission rate:** A household census will be obtained at the time of enrollment, and information about household contacts symptoms will be obtained during daily surveys to determine household transmission rate.

- Adverse Events:** Occurrence of side effects such as bloating, gas, intestinal rumbling, diarrhea, blood in stool, abdominal pain, abdominal cramps nausea, vomiting, loss of appetite, abnormal taste, heartburn, constipation, skin rash, fever, nasal congestion, sore throat, cough, headache, muscle aches, chills, etc..

The overall significance level for statistical tests on the secondary outcomes will be set at 0.05. Holm's method will be used to adjust for multiple comparisons. The continuous variables of duration of diarrhea and duration of vomiting (measured in hours and analyzed with a Van Elteren test), will be stratified by clinical center. Similarly, the number of days the child is absent from daycare and the caregiver is absent from work will be analyzed with a Van Elteren test, stratified by clinical center and etiology.

Dichotomous outcomes to be evaluated include emergency department acute gastroenteritis-related revisits, intravenous rehydration, and hospitalization. Additional analyses involving these outcomes will include linear and logistic regression models that adjust for possible effects of baseline characteristics.

### 5.3 Sample Size Calculations and Statistical Power

The primary analysis will be performed on a binary outcome: development of moderate-to-severe disease. The power of this analysis is based on the proportion of patients with moderate-to-severe disease. Our pilot data indicate that 25% of patients will have moderate to severe disease during the course of their illness. Furthermore expert surveys indicated that an absolute risk reduction of 10% would constitute a minimal clinically-important difference (MCID). Therefore our sample size calculation assumed a 25% event rate in the control group for which we desire to detect an absolute beneficial treatment effect of 10% with 90% power. Using a two-sided type I error ( $\alpha$ ) of 0.05 and the hypothesized proportions yields a required total sample size of 670 patients. Our expected power, should we find different event rates in our 2 groups, is displayed in Table 2 on the next page.

Based on previous work by our group, we assumed a 10% loss to follow up ( $670/0.90 = 744$ ), 5% drop out, and 3% drop in (caregivers who buy a probiotic agent to administer to their child) rate ( $744/(0.92)^2 = 879$ ). Adjustment for O'Brien-Fleming monitoring boundaries requires a further 2% increase. Thus, the total number randomized (final sample size) will be 897.

Outcome Control	Outcome Intervention	% Difference	Power
0.30	0.21	9%	0.76
0.30	0.20	10%	0.85
0.25	0.15	10%	0.90
0.25	0.16	9%	0.82
0.25	0.17	8%	0.72
0.20	0.10	10%	0.95
0.20	0.12	8%	0.81
0.20	0.13	7%	0.69

Table 2: Power Analysis

### 5.3.1 Enrichment Design

The above study design and power analysis are based on the assumption of homogeneous treatment effect. We may also incorporate an enrichment design to restore the statistical power in case the presence of a subpopulation with a substantially low treatment effect is identified. We are particularly interested in two potential subpopulations: participants with  $<2$  days of symptoms and those with  $\geq 2$  days of symptoms. Based on our pilot data, each subpopulation accounts for approximately 50% of the total population. The decision for enrollment modification will be made at the first interim analysis for efficacy. Specifically, three statistics (based on a normal approximation of binomial distribution, or z-statistics) will be calculated to compare the primary efficacy endpoint between treatment and control groups for subjects in the total population and the two subpopulations, respectively. If the z-statistic from a subpopulation is  $<0.3$  and also smaller than that in the total population, subjects from this subpopulation will no longer be considered in the subsequent enrollment. All subjects, regardless of symptom duration will be included in the final analyses. Our simulation studies have shown that such an enrichment design can increase the power considerably when the treatment effects are different across subpopulations, while it will have little impact on power when the treatment effects are similar.

### 5.3.2 Sub-group Analyses

The presence of a Modified Vesikari Score  $\geq 9$  will be analyzed by age  $<1$  year, duration of symptoms, breast-feeding status, antibiotic usage, rotavirus and norovirus positivity. A subgroup effect will be considered significant if the interaction between subgroup and treatment in a logistic regression model is significant at a Bonferroni-corrected level.

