## 3 Study Design and Methods

### 3.1 Overall Study Design

The Probiotics trial has a parallel group design with a placebo control. We will not describe specifics about the active agent or placebo here, as these are contained in the protocol. We will refer to the two trial arms as Active and Placebo. Study participants will be randomized to Active or Placebo, each having equal allocation. Treatment with the assigned therapy is to commence immediately following randomization. The primary analysis will be performed on an intention-to-treat basis. We will also use an enrichment design, possibly modifying the eligibility criteria of the trial based on interim results.

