### 4.3 Enrichment Design

The study design and power analysis described are based on the assumption of homogeneous treatment effect. We may also incorporate an enrichment design to restore the statistical power in case the presence of a subpopulation with a substantially low treatment effect is identified [1]. We are particularly interested in two potential subpopulations: participants with <48 hours of symptoms prior to presentation and those with 48 hours or more of symptoms. Based on pilot data, each subpopulation accounts for approximately 50% of the total population. The decision for enrollment modification will be made at the first interim analysis for efficacy. Specifically, three Mantel-Haenszel z-statistics will be calculated to compare the primary efficacy outcome between Active and Placebo groups for subjects in the total population and the two subpopulations, respectively. Denote these z-statistics as  $Z_{0,1}$ ,  $Z_{<48,1}$ , and  $Z_{>48,1}$ . Note that a positive z-statistic sign will be used to indicate superiority of probiotic relative to placebo.

First,  $Z_{0,1}$  will be compared to the O'Brien-Fleming boundary to determine whether the trial should be discontinued for efficacy (as described in Section 6.2). If the boundary is not crossed, or if the DSMB will otherwise recommend continuation of the trial, all three z-statistics will be considered. If  $Z_{0,1}$  is larger than both  $Z_{<48,1}$  and  $Z_{>48,1}$ , or if both  $Z_{<48,1}$  and  $Z_{>48,1}$  are  $>0.3$ , accrual will continue as before. Otherwise, future patients will be recruited only from the subpopulation with the larger z-statistic. All subjects, regardless of symptom duration will be included in the final analyses. At the second interim analysis and the final analysis (or any additional unplanned interim analysis), the following method will be used to test for efficacy.

Let  $Z_2$  be the Mantel-Haenszel z-statistic that is based only on subjects enrolled since the first interim analysis. Then, the final test statistic to be used is a weighted sum of the statistics from each stage:

$$Z = \left( \frac{n_1}{n_1 + n_2} \right) Z_{0,1} + \left( \frac{n_2}{n_1 + n_2} \right) Z_2,$$

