## 5.5 Planned Subgroups, Interactions, and Covariates

There are three subgroup factors prespecified for formal analysis in this trial:

1. Age (under 1 year versus 1 and older)
2. Antibiotic useage during the 14 days prior to ED visit,
3. Infectious agent: virus, bacteria, parasite, or other/unidentified.

We will also consider the factor used to randomize, duration of symptoms (<48 hours vs. 48 hours or more), in subgroup analyses.

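### If accrual is restricted on symptom duration, the dropped group's estimate is biased toward no benefit, and neither document qualifies the duration subgroup analysis for this

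*Combined protocol and SAP*

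**What the plan says.** **Enrichment.** Protocol 5.3.1 compares the arms within two duration groups (under 2 days of symptoms, and 2 days or more) at the first efficacy interim. If a group's z-statistic is below 0.3 and below that of the total population, "subjects from this subpopulation will no longer be considered in the subsequent enrollment". SAP 4.3 continues as before if the total z exceeds both group values or both exceed 0.3. "Otherwise, future patients will be recruited only from the subpopulation with the larger z-statistic". Both documents keep every enrolled child in the final analyses.

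**Subgroups.** Protocol 5.3.2, with the same text in V1.0 and V3.0, names age under 1 year and "duration of symptoms, breast-feeding status, antibiotic usage, rotavirus and norovirus positivity". A subgroup effect is declared from the interaction term of a logistic model at a Bonferroni level, with no divisor given. SAP 7.6 allows a declaration at 0.05/3 for age, antibiotic use and infectious agent only. SAP 5.5 then adds: "We will also consider the factor used to randomize, duration of symptoms". It gives no model, level or decision rule for that factor.

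**Adjustment.** The only statistic built for the adaptation is the staged Z in SAP 4.3, which serves the overall efficacy test. Nothing adjusts or qualifies the comparison by duration.

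**The concern.** After a restriction the two duration groups carry different kinds of data. The dropped group has only the interim data whose low result caused it to be dropped. The kept group has its interim data plus all later accrual. A low interim result in the dropped group therefore cannot move back toward the truth, while the kept group's result can.

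An ordinary logistic interaction treats both groups as if their sizes had been fixed in advance. Even without a significant interaction, results by duration will be reported, and the dropped group's figure will look like absence of benefit or harm. SAP 4.3 says that a significant overall result indicates efficacy in the population enrolled after the first interim. Readers will naturally ask next whether the dropped children fail to benefit, and the by-duration result answers that question with a selected estimate.

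**Working it through.** **1. The plan's own figures.** The plan says that "our sample size calculation assumed a 25% event rate in the control group" and that "we desire to detect an absolute beneficial treatment effect of 10% with 90% power", two-sided 0.05, equal allocation. Per arm:

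n = [1.960 × √(2 × 0.20 × 0.80) + 1.282 × √(0.25 × 0.75 + 0.15 × 0.85)]² / 0.10² = (1.109 + 0.719)² / 0.01 ≈ 334.2, so 335 per arm and 670 in total, as stated. Then 670/0.90 = 744, 744/0.92² = 879, and 879 × 1.02 = 897, also as stated.

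**2. Design effect as an odds ratio.** (0.15/0.85)/(0.25/0.75) = 0.53. Applied to the untreated rates in SAP 4.3 (30% and 20%), it gives 0.4286 × 0.53 = 0.227, or 18.5%, and 0.25 × 0.53 = 0.1325, or 11.7%. The mean is 15.1%, so this is the plan's design effect, equal in both groups on the scale of the logistic model.

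**3. Mechanism by hand.** Look at 350 children (SAP 6.1), 90% evaluable (protocol 5.4.4), groups of equal size: 315/4 = 78.75 per arm and group. With 25% against 15%:

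- Standard error = √(0.20 × 0.80 × 2/78.75) = 0.0638; expected z = 0.10/0.0638 = 1.57.
- A z below 0.3 lies 1.27 standard errors low, probability 0.102. For at least one group: 2 × 0.102 − 0.102² = 0.19.
- Mean z given z < 0.3: 1.57 − 0.178/0.102 = −0.17. As a risk reduction: −0.17 × 0.0638 = −0.011, about −1.1 points when the truth is +10.

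**4. Simulation.** 400,000 trials per scenario: SAP untreated rates, look at 350, stop at 0.00065 (SAP 6.2), SAP 4.3 rule, N = 900, 90% evaluable. The final test is the Wald interaction on the log-odds scale, equivalent to the two-group logistic interaction. The level is 0.05/6 = 0.0083; the six factors are an assumption (five would give 0.01).

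| True common OR | Trials restricted | Mean OR, dropped group | False interaction, restricted trials | False interaction, all trials |
|---|---|---|---|---|
| 0.53 | about 20% | 1.09 | 4% | 1.1% |
| 0.75 | about 51%* | 1.19 | 1.4% | 0.9% |
| 1.0 | about 83% | 1.35 | 0.8%* | 0.7%* |

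*From runs with every child evaluable and N = 970.

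- At 0.53 the restriction rate lies inside the 0.05 to 0.35 that SAP 4.3 gives for a homogeneous effect.
- The kept group's mean odds ratio at 0.53 is 0.52, so the ratio of odds ratios is 0.52/1.09 = 0.48 instead of 1. With every child evaluable, the kept group's mean risk reduction is 5.4 points against a true 5.0 at 0.75, and 0.6 against 0 at 1.0.
- Without any restriction rule, the error at 0.53 is 0.74% at the 0.0083 level.
- At 0.53, all the false interactions in restricted trials under the SAP rule go against the dropped group.
- The protocol 5.3.1 rule and N = 970 give nearly the same results. With every child evaluable, restriction at the design effect falls to 15–17%, and the dropped group's mean risk reduction is −1.1 to −1.2 points against a true 9.5 to 10, close to the hand calculation.

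The second interim look was not modelled.

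**The case against.** **Status of the test.** The SAP does not formally test duration: 7.6 confines declarations to three other factors and urges caution even there. The formal test stands only in the protocol. This limits the point but does not remove it, because both protocol versions list duration and SAP 5.5 brings it back without a rule.

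**Size of the error.** A reader might infer that false duration interactions would be common. At 0.53 the error in restricted trials is 23% at 0.05 and 8% at 0.017, but neither document assigns those levels to duration. At the protocol's level, if six factors are meant, about 96% of wrongly restricted trials still declare no interaction. Over all trials the excess is 1.1 − 0.83 ≈ 0.3 points. At 0.75 the overall error is essentially nominal, and with no effect there is no inflation. This objection stands. The bias in the dropped group's estimate is the larger problem, and it is present in all three scenarios.

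**Disclosure.** SAP 4.3 admits that a restriction can occur under a homogeneous effect, and protocol 5.3.1 words enrichment as optional. Neither statement warns about the by-duration results.

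**Dropping the analysis altogether.** One might conclude that duration must not be tested after a restriction. The figures do not support a ban. With odds ratios of 0.40 and 1.0 in the two groups, about 62% of trials are restricted, and the interaction test then has roughly 44–50% power at 0.0083. A p-value that accounts for the design can keep part of that.

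**Conclusion.** The point holds in a limited form. After a restriction, the dropped group's estimate is biased toward no benefit: mean odds ratio about 1.09, 1.19 or 1.35 for a true 0.53, 0.75 or 1.0. The nominal interaction test is inflated mainly when the treatment works equally well in both groups at the design size. There the error is about 4% in restricted trials, roughly five times nominal (4/0.83 = 4.8), and 1.1% over all trials against 0.83%.

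The result rests on the SAP's rates and group sizes, 90% evaluable, a six-factor Bonferroni level, and homogeneity meaning one common odds ratio.

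A reader might go further and infer that the trial's main conclusion is compromised. The documents do not support that. The primary efficacy test does not use the duration interaction, and the kept group's estimate is nearly unbiased. What needs correcting is a subgroup rule that yields a biased result in one branch of the design, and a mismatch between protocol and SAP over whether duration is formally tested.

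**What to change.** First, give duration one status. Protocol 5.3.2 treats it as formally tested, while SAP 5.5 and 7.6 leave it outside the formal family. State which applies, with the divisor for the level.

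Second, add to protocol 5.3.2 and SAP 5.5:

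> If accrual was restricted on duration of symptoms, the nominal logistic interaction p-value for duration is not used to declare a subgroup effect. Results by duration are shown separately for children enrolled before and after the first interim, with a statement that the dropped group's estimate was selected at the interim. Any interaction p-value is taken from simulation of the whole adaptive design under a common odds ratio, over a range of common odds ratios.

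The range matters because the inflation depends on the true common effect. The cost is a few sentences, some simulation beyond that already described in SAP 4.3, and some loss of power for the duration interaction in the restricted branch. Sample size, enrichment rule and primary analysis stay as they are.
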